## 1.0 OBJECTIVES

### Primary Objective

Estimate the efficacy of combination treatment with encorafenib and binimetinib, as measured by response rate (RANO criteria), in patients with recurrent BRAF V600E/K-mutated malignant glioma (MG) and anaplastic pleomorphic xanthoastrocytoma (PXAs).

### Secondary Objectives

1. Estimate efficacy as measured by progression-free survival in subjects with recurrent malignant glioma or anaplastic PXA containing a BRAF-V600E/K mutation who receive drug.
2. Evaluate duration of response in subjects who have a partial or complete response.
3. Quantify the time-to-response among subjects who have a radiologic response.
4. Estimate efficacy as measured by overall survival in subjects with recurrent malignant glioma or anaplastic PXA containing a BRAF-V600E/K mutation who receive drug.
5. Characterize the toxicity profile of the combination of encorafenib and binimetinib in this patient population.

### Exploratory Objectives

1. Estimate efficacy as measured by response rate, progression free survival, and overall survival in study participants with tumors other than MG and anaplastic PXA (cohort 3).
2. Estimate encorafenib and binimetinib concentrations in enhancing brain tissue and cerebrospinal fluid from a surgical cohort.
3. Explore putative mechanisms of resistance to encorafenib and binimetinib in BRAF-V600E/K mutated gliomas from an upfront surgical cohort and in patients who progress on study and undergo a clinically-indicated surgery.
4. Analyze the functional inhibition of the ERK signaling pathway in tumor tissue from a surgical cohort of patients treated with encorafenib and binimetinib, and correlate serum concentrations with changes in pathway activity.
5. Measure BRAF-V600 DNA mutant fraction in CSF and plasma over time while participants are receiving treatment.

## 2.0 BACKGROUND AND RATIONALE

### 2.1 BRAF Mutations in Gliomas

BRAF is one of 3 RAF-kinase isoforms (the others are ARAF and CRAF). All three are activated by dimerization, and induce MEK1 and MEK2 (MEK1/2) phosphorylation, which then activates ERK1 and ERK2 (ERK1/2). ERK1/2 translocates into the nucleus and regulates targets associated with proliferation, differentiation, and survival.(1) BRAF can be constitutively activated by point mutations removing the need for dimerization or by fusions with other kinases (KIAA1549-BRAF).(2) The *BRAF* V600 point mutation in particular is located within the kinase domain and allows constitutive activation of the kinase by removing inhibitory domain and prerequisite of dimerization for activity. This results in increased activation of the ERK signaling pathway and leads to cell proliferation and survival.(2)

While BRAF fusions are relatively common in pediatric gliomas, *BRAF* V600 mutations are also present in some adult gliomas. *BRAF* V600 mutations have been described in a variety of adult and pediatric gliomas including pleomorphic xanthoastrocytomas (PXA) (60-80%), gangliogliomas (20-70%), pilocytic astrocytomas (9-10%), low grade gliomas (5-15%) and glioblastomas (GBM) (1-5%).(3-5) While mutation is less common in adult GBM, it is relatively enriched for in the epithelioid subtype of GBM,(5, 6) and possibly in low grade astrocytomas as well (5-15%).(7) Despite a relatively low incidence in adults, the potential for targeted therapy makes *BRAF* V600 mutations in recurrent gliomas significant, as prognosis is poor and treatment options are very limited.

Current treatment for high-grade gliomas in adults is maximal safe surgical resection, followed by radiation with concurrent temozolomide, then adjuvant temozolomide. (8) Low-grade gliomas may be treated with an alternative chemotherapy regiment or radiation alone. Despite this, the average life expectancy for patients with glioblastoma is less than 18 months even with standard therapy, which was approved by the FDA thirteen years ago. While there is a significant amount of research underway for novel treatments, overall these have been disappointing to date. Recent advances in molecular diagnostics have revealed different glioblastoma subtypes that may have different driver mutations. (9)

The overall effect of *BRAF* mutations on the natural history of gliomas is unclear. A retrospective study of young adults (age 18-35) with GBM found BRAF mutations are associated with improved prognosis as compared to BRAF-WT tumors.(10) A similar result was found in a recent meta-analysis, which found BRAF-V600 mutations correlated with improved overall survival for young adults and low grade gliomas, but have no effect on prognosis in GBM in adults >35 years old, though the sample size was quite small.(11) In PXAs, BRAF mutations are associated with a longer overall survival in one analysis,(12) though not in another.(13)

## 2.2 Encorafenib

Encorafenib [methyl *N*-{(2*S*)-1-[(4-{3-[5-chloro-2-fluoro-3(methanesulfonamido) phenyl]-1-(propan-2-yl)-1*H*-pyrazol-4-yl}pyrimidin-2-yl)amino] propan-2yl} carbamate] is a potent BRAF kinase inhibitor that is orally bioavailable and FDA approved in combination with binimetinib for the treatment of unresectable or metastatic melanoma with BRAF V600E or K mutations. It inhibits all RAF isoforms, but is most potent against the *BRAF* V600E mutations (IC50 = 0.35 nM), but also against wild-type (wt) BRAF and CRAF (IC50 0.47 nM and 0.3 nM, respectively) in *in vitro* cell-free assays. (14)

### Clinical Pharmacokinetics (PK) and Drug-drug Interactions of Encorafenib

The pharmacokinetics (PK) of encorafenib were studied in healthy subjects and patients with solid tumors, including advanced and unresectable or metastatic cutaneous melanoma harboring a *BRAF* V600E or K mutation. After repeat once-daily dosing, steady-state conditions were reached within 15 days, exposure being approximately 50% lower compared to Day 1, with a median half-life ~4 hours, and moderate intersubject variability (percent coefficient of variation [%CV]) of area under the curve (AUC; 12.3% to 68.9% over a range of doses). The PK of encorafenib has been shown to be approximately dose proportional after multiple doses, with any deviation from dose proportionality likely due to auto-induction of CYP3A4.

The human ADME study in healthy subjects showed that encorafenib is at least 86% absorbed and has a preferential distribution to plasma as compared to blood. Encorafenib was mainly eliminated via metabolism, with low levels of unchanged encorafenib detected in urine and feces. The dose was equally recovered in urine and feces (47.2% in each matrix) and the renal clearance was estimated to be 1.8%.

Results from a food-effect clinical study in healthy subjects have indicated that the influence of food on the PK of encorafenib is mild and not clinically relevant; therefore, encorafenib can be taken without regard to food. In combination studies, when administered with binimetinib, PK parameters of encorafenib were similar to those observed in the single-agent study.

## 2.3 Binimetinib

Binimetinib is an adenosine triphosphate (ATP)-uncompetitive inhibitor of MEK1 and MEK2. In cell-free systems, binimetinib inhibits MEK1 and MEK2 with half maximal inhibitory concentration (IC50) values of 12 nM and 46 nM, respectively, on purified enzymes. The IC50 value of the active metabolite of binimetinib, AR00426032, was 7.1 nM. It is approved by the FDA in combination with encorafenib for the treatment of unresectable or metastatic melanoma with BRAF V600E or K mutations. (15)

### Clinical Pharmacokinetics (PK) and Drug-Drug Interactions of Binimetinib

The PK of binimetinib are characterized by moderate to high variability, accumulation of approximately 1.5-fold, and steady state concentrations reached within 15 days. Binimetinib has been shown to be approximately dose proportional (Clinical Study Pfizer -162-111). The human ADME study indicated that approximately 50% of binimetinib dose was absorbed. The

primary metabolic pathways include glucuronication (up to 61.2% via UGT1A1), N-dealkylation (up to 17.8% via CYP1A2 and CYP2C19) and amide hydrolysis. The excretion route was 31.7% of unchanged binimetinib in feces and 18.4% in urine. Estimated renal clearance of unchanged binimetinib was 6.3% of total dose. The impact of UGT1A1 inhibitors or inducers has not been clinically assessed.

Food-effect clinical studies have indicated that the influence of food on the PK of binimetinib is mild and not clinically relevant; therefore, binimetinib can be taken with food.

## 2.4 Combination Therapy

Mathematical models support the fact that resistance to two different drugs, given serially, emerges faster than to the two drugs given simultaneously. (16) Unfortunately, resistance to BRAF inhibitors emerges in an average of 5-7 months in patients with melanoma. (17, 18) This occurs by a variety of different mechanisms including secondary mutations in BRAF, truncations, upregulation of other RAS/RAF family members, PI3K activation, PTEN loss, or RTK upregulation. (19-23) There have been attempts to avoid resistance by blocking MEK1/2, which is immediately downstream of BRAF, thereby making it more difficult for tumors to escape inhibition. Early studies showed that if a BRAF inhibitor is followed by a MEK inhibitor at the time of tumor progression, there is only a marginal improvement in survival (1.8mo). (24) More recently, the upfront combination of BRAF and MEK inhibitors has resulted in improved progression free survival as compared to monotherapy, and three different combinations of BRAF and MEK inhibitors are approved by the FDA for advanced-stage melanoma, including encorafenib and binimetinib (Table 1). (25-27) Encorafenib and binimetinib are approved by the FDA for combination therapy in patients with advanced or metastatic melanoma with an E or K mutation. (14, 15) The phase 3 COLUMBUS trial in advanced / metastatic melanoma with BRAF V600E or K mutations compared encorafenib plus binimetinib against vemurafenib alone and showed a progression free survival rate of 14.9 versus 7.3 months. (27) Overall survival was also favorable in the combination group, with median survival of 33.6 months with combination treatment and 16.9 months with vemurafenib alone. (28)

Study	Population	Therapy
CMEK162X2110, Phase 1b/2 (n=189)	BRAF V600E/K mutated advanced solid tumor	Encorafenib plus binimetinib
CLGX818X2109, Phase 2 (n=158)	Advanced melanoma with BRAF V600 mutation	Encorafenib plus binimetinib
CMEK162B2301, Phase 3 (n=921)	Advanced melanoma with BRAF V600 mutation	Encorafenib plus binimetinib vs. vemurafenib or encorafenib

Table 1: Compilation of clinical trials assessing encorafenib and binimetinib in patients with advanced cancer.

## **Clinical Pharmacokinetics (PK) of Combination Therapy**

Administration of 45 mg binimetinib twice daily with escalating doses of daily encorafenib showed no distinct trend towards change in Cmax or AUC of binimetinib or encorafenib (compared to single-agent PK studies), per investigator brochure.

### **Blood Brain Barrier Penetration of Encorafenib and Binimetinib**

Encorafenib is a P-glycoprotein (P-gp) substrate and an inhibitor of breast cancer resistance protein (BCRP), while binimetinib is a P-gp and BCRP substrate. Due to the function of the blood-brain barrier, the penetration of a drug into the brain depends on its intrinsic membrane permeability and its susceptibility to active efflux.(29) Although encorafenib and binimetinib have high intrinsic membrane permeability, efflux transporters may result in reduced brain concentrations for both.

Animal models have limited utility in predicting the effect of efflux transporter proteins on human brain concentrations. (29, 30) For example, dabrafenib and trametinib are efflux transporter substrates thought to have limited brain penetration based on nonclinical data, yet the combination had clinical activity in patients with melanoma brain metastasis in the COMBI-MB study. (31-33)

## 2.6 Correlative Studies Background

### BRAF-V600 DNA Mutant Fraction in CSF and Plasma

Circulating tumor DNA (ctDNA) detected in plasma is becoming a powerful tool for detecting remission or progression in systemic cancers. (46-50) However, ctDNA is a generally insensitive tool for brain tumors. Our collaborators have demonstrated that cerebrospinal fluid (CSF) may be a more sensitive means of detecting circulating DNA (CSF-tDNA) than blood (Figure 2). (47) We intend to determine how sensitively and reliably ctDNA mutations can be detected in patients undergoing a uniform treatment regimen. ctDNA will be quantified from both CSF and plasma, and analyzed over time in patients who contribute multiple samples.

[figure not shown]

Figure 2: Detection of CSF-tDNA from primary brain tumors as derived from ventricular or lumbar CSF. Detected in 18/19 HGG and 8/15 LGG

### 3.0 PATIENT ELIGIBILITY CRITERIA

#### 3.1 Patient Sample

Sample Size:

Minimum: 28 patients / Maximum: 62 patients

Accrual Rate:

1 patient per month

Gender:

Male and female

Age:

Patients must be at least 18 years of age.

Race:

Minorities will be actively recruited. No exclusion to this study will be based on race or ethnicity.

#### PLANNED ENROLLMENT REPORT

Racial Categories	Ethnic Categories				Total
	Not Hispanic or Latino		Hispanic or Latino		
	Female	Male	Female	Male	
American Indian/ Alaska Native	0	0	0	0	0
Asian	2	5	0	0	7
Native Hawaiian or Other Pacific Islander	0	0	0	0	0
Black or African American	4	5	0	0	9
White	14	21	3	8	46
More Than One Race	0	0	0	0	0
Total	20	31	3	7	62

### 3.2 Inclusion Criteria

Patients eligible for inclusion in this study must meet all the following criteria within 30 days unless otherwise specified:

1. Subjects must have histologically confirmed high-grade glioma at diagnosis or recurrence (including but not limited to glioblastoma (GBM), anaplastic astrocytoma (AA), and gliosarcoma), or other high-grade primary brain tumor [including but not limited to anaplastic pleomorphic xanthoastrocytoma (aPXA), anaplastic ependymoma, and anaplastic ganglioglioma (AG)], that is recurrent after irradiation.
2. Patients must have a previously documented BRAF-V600 E or K mutation as performed by PCR or next generation sequencing in a CLIA-approved laboratory (including but not limited to Caris and FoundationOne).
3. Patients must have measurable (defined by at least 1 cm x 1 cm) contrast-enhancing disease by MRI imaging within 30 days of starting treatment.
4. The following intervals from previous treatments are required to be eligible:
  - 12 weeks from the completion of radiation.
  - 16 weeks from an anti-VEGF therapy
  - 4 weeks from a nitrosourea chemotherapy
  - 3 weeks from a non-nitrosourea chemotherapy
  - 2 weeks or 5 half-lives from any investigational (not FDA-approved) agents
  - 2 weeks from administration of a non-cytotoxic, FDA-approved agent (e.g., erlotinib, hydroxychloroquine, etc.)
5. Patients must be 18 years of age or older.
6. Patients must have a Karnofsky Performance (KPS) Status  $\geq 60\%$ .
7. Patients must have the following organ and marrow function within 30 days of starting treatment:

Absolute neutrophil count	$\geq 1,000/\text{mcL}$
Platelets	$\geq 100,000/\text{mcL}$
Hemoglobin	$\geq 9 \text{ g/dL}$
Total bilirubin	$\leq 1.5 \times$ institutional upper limit of normal (ULN) OR total bilirubin $>1.5 \times$ ULN with direct bilirubin $< 1.5 \times$ ULN;
AST (SGOT)/ALT (SGPT)	$\leq 3 \times$ institutional ULN
Creatinine	$\leq 1.5 \times$ institutional ULN
	OR
Creatinine clearance	$\geq 50 \text{ ml/min/1.73m}^2$ for patients with creatinine levels above institutional normal
APTT or PTT	$\leq 1.5 \times$ institutional ULN; subjects on anticoagulation may be permitted to participate
LVEF	$\geq 50\%$ as determined by MUGA or ECHO
QTc Interval	$< 480 \text{ ms}$ per triplicate averaged baseline ECG.

8. Patients must be able to provide written informed consent.
9. Women of childbearing potential must have a negative serum pregnancy test prior to study start. Women of childbearing potential must agree to use adequate contraception (intrauterine device, barrier, or other *non*-hormonal method of birth control; or abstinence) and not to donate ova from screening through 30 days after the last dose of study drug. Male participants must also agree to use adequate contraception and not to donate sperm from screening until 90 days after the last dose of study drug.
10. Patients must be maintained on a stable or decreasing dose of systemic corticosteroid regimen (no increase for 5 days) prior to baseline MRI. Topical and inhaled steroid treatment is allowed.
11. Patients must have no concurrent malignancy except curatively treated basal or squamous cell carcinoma of the skin or carcinoma in situ of the cervix, breast, or bladder. Patients with other malignancies must be disease-free for  $\geq 2$  years.
12. Patients must be able to swallow tablets and capsules.
13. Patients must have a tumor tissue form completed and signed by a pathologist; sites must agree to provide this form within 14 days after treatment start (see Section [9.6.4](#)). The tumor tissue form must indicate availability of archived tissue. The archived tissue should be from the most recent tumor resection, demonstrating active tumor when sufficient tissue is available. If sufficient tissue is not available from the most recent surgery, then tissue from an earlier surgery is acceptable, if available, including from the initial resection at diagnosis.

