## **8.0 RESPONSE ASSESSMENT / SAFETY AND QUALITY ASSURANCE**

### **8.1 Criteria for Response Assessment**

Patients with measurable enhancing disease will be assessed by the high grade glioma (HGG) RANO (radiographic assessment in neuro-oncology) criteria, while patients with no measurable enhancing mass and only T2/FLAIR abnormalities will be assessed using the low grade glioma (LGG) RANO criteria. For the purposes of this study, subjects should be re-evaluated at the end of every 2 cycles (approximately every 8 weeks) with a contrast-enhanced cranial MRI scan. The response will be determined as outlined in the RANO criteria below.

*Measurable Disease on HGG RANO.* Bi-dimensionally, contrast-enhancing, measurable lesions with clearly defined margins by MRI scan, with a minimal size of 1 cm x 1 cm, and visible on 2 axial slices which are at least 5 mm apart with 0 mm skip. If there are >2 lesions (multifocal) at baseline, the investigator must choose the largest two to be followed before a participant is entered on study. The remaining lesions will be considered non-measurable for the purpose of objective response determination. Unless progression is observed, objective response can only be determined when all measurable and non-measurable lesions are assessed.

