**Complete Response – CR (requires *all* of the following):**

- a) Complete disappearance of all enhancing measurable and non-measurable disease, including T2 or FLAIR hyperintense lesions, sustained for at least 4 weeks. In the absence of a confirming scan 4 weeks later, this scan will be considered only stable disease.
- b) No new lesions.
- c) All measurable and non-measurable lesions, including T2/FLAIR hyperintense lesions, must be assessed using the same techniques as baseline.
- d) Subjects must be off corticosteroids (or on physiologic replacement doses only).
- e) Stable or improved non-enhancing (T2/FLAIR) lesions.
- f) Stable or improved clinically.

**Note:** Subjects with non-measurable disease cannot have a complete response. The best response possible is stable disease.

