**Partial Response – PR (requires *all* of the following):**

- a) Greater than or equal to 50% decrease compared to baseline in the sum of products of perpendicular diameters of all measurable enhancing lesions (HGG RANO) or T2 hyperintense lesions (LGG RANO), sustained for at least 4 weeks. In the absence of a confirming scan 4 weeks later, this scan will be considered only stable disease.
- b) No progression of non-measurable disease if HGG RANO is used.
- c) No new enhancing or non-enhancing lesions.
- d) All measurable and non-measurable lesions must be assessed using the same techniques as baseline.
- e) The corticosteroid dose at the time of the scan evaluation should be no greater than the dose at time of baseline scan.
- f) Stable or improved non-enhancing (T2/FLAIR) lesions on same or lower dose of corticosteroids compared to baseline scan if using HGG RANO.
- g) Stable or improved clinically.

**Note:** Subjects with non-measurable disease cannot have a partial response. The best response possible is stable disease.

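### The entry criterion defines measurable disease more loosely than the response criteria, so a patient with no lesion that meets Section 8.1 can be enrolled but cannot be scored as a responder

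*Combined protocol and SAP*

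**What the plan says.** Section 3.2, criterion 3, sets the entry standard: "Patients must have measurable (defined by at least 1 cm x 1 cm) contrast-enhancing disease by MRI imaging within 30 days of starting treatment". The bracket is a self-contained definition by size, and the criterion does not refer to Section 8.1.

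Section 8.1 defines measurable disease under HGG RANO as "measurable lesions with clearly defined margins by MRI scan, with a minimal size of 1 cm x 1 cm", and adds that the lesion must be "visible on 2 axial slices which are at least 5 mm apart with 0 mm skip".

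The consequence of not meeting that definition is explicit. The PR note reads "Subjects with non-measurable disease cannot have a partial response. The best response possible is stable disease", and the CR note reads "Subjects with non-measurable disease cannot have a complete response. The best response possible is stable disease".

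Section 11.2 sets the decision rules for each primary cohort. Stage 1 stops at 1 or fewer responses in the initial 14 patients, and the final rule asks for at least 5 responses among 23 patients described as evaluable. The same section estimates the response rate over all patients in the cohort. No definition of evaluable is given.

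**The concern.** The primary endpoint is RANO response, and the two sections that decide who can reach it use different definitions of the same word. A site that follows criterion 3 exactly may enrol a patient whose only enhancing lesion has two diameters of at least 1 cm but has indistinct margins or fails the two-slice test. Under Section 8.1 that patient has no measurable disease and enters with stable disease as the best attainable result.

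If such patients are counted, the observed response rate is pulled down for a reason unrelated to drug activity, and an active regimen is more likely to be stopped at 14 or declared negative at 23. With accrual expected at one patient per month across 11 institutions, a cohort closed wrongly would be slow to rebuild.

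**Working it through.** **Step 1. Does another provision close the gap?**

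- *LGG RANO route (Section 8.1).* It applies where "patients with no measurable enhancing mass and only T2/FLAIR abnormalities will be assessed using the low grade glioma (LGG) RANO criteria". A patient with an enhancing lesion that fails on margins or slices does not have T2/FLAIR abnormality only, so this route does not fit.
- *Lesion choice before entry (Section 8.1).* The instruction that "the investigator must choose the largest two to be followed before a participant is entered on study" applies only with more than two lesions. It selects targets and does not test eligibility.
- *Registration (Section 7.3).* Sites verify the eligibility criteria, which means the Section 3.2 wording.
- *Replacement (Section 4.1).* The only replacement rule concerns surgical-arm histopathology.
- *Central review (Section 8.2).* It covers scans already called PR or CR locally and is not a baseline check.

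None of these requires the Section 8.1 definition at entry for every patient.

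**Step 2. Reproduce the plan's own figures.** Inputs from Section 11.2: null rate 10%, alternative 30%, n1 = 14 (stop at 1 or fewer), N = 23 (success at 5 or more).

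Formula: P(success) = Σ over x ≥ 2 of P(X1 = x) × P(X2 ≥ max(0, 5 − x)), with X1 ~ Bin(14, p) and X2 ~ Bin(9, p).

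At p = 0.30:

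- x = 2: 0.1134 × 0.5372 = 0.0609
- x = 3: 0.1943 × 0.8040 = 0.1562
- x = 4: 0.2290 × 0.9596 = 0.2198
- x ≥ 5: 0.4158 × 1 = 0.4158
- Sum: 0.853 (stated: at least 85%)

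At p = 0.10, P(success) = 0.070 (stated ceiling 10%), and P(X1 ≤ 1) = 0.585 (stated: at least 0.58). The plan's figures reproduce. The power margin is 0.853 − 0.850 = 0.003.

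**Step 3. Fix some patients as non-responders.** Let k1 and k2 be the numbers who cannot be scored in stages 1 and 2. Replace 14 by 14 − k1 and 9 by 9 − k2, and leave the thresholds unchanged. The documents give no values for k1 and k2, so these are assumed.

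Example, k1 = 1 and k2 = 0 at p = 0.30: 0.1388 × 0.5372 + 0.2181 × 0.8040 + 0.2337 × 0.9596 + 0.3457 = 0.820.

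| k1, k2 | Power at 30% | Stage 1 stop at 30% | Type I error at 10% |
|---|---|---|---|
| 0, 0 | 0.853 | 0.047 | 0.070 |
| 1, 0 | 0.820 | 0.064 | 0.059 |
| 0, 1 | 0.827 | 0.047 | 0.060 |
| 1, 1 | 0.791 | 0.064 | 0.050 |
| 2, 1 | 0.748 | 0.085 | 0.041 |

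The expected response rate at a true 30% falls to 30% × 22/23 = 28.7% with one such patient and 30% × 20/23 = 26.1% with three.

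**Step 4. Which rules do these figures apply to?** The response rate uses all patients in the cohort, so these patients are in its denominator. The stage 1 rule speaks of the initial 14 patients without qualification, so on its face they are counted there too. The final rule speaks of evaluable patients. If that word excludes them and they are replaced, they do not reduce the number of scorable patients in the final 23.

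**The case against.** The strongest reply is that the final rule is written for evaluable patients. If a patient without Section 8.1 disease is not evaluable, that patient falls outside the 23. If the same exclusion also applied at stage 1, power would stay at 0.853. This stands as far as it goes: a reader might infer that such patients are certainly built into the 5-of-23 count, and the text does not settle that. It does not settle the opposite either, and the word is absent from the stage 1 rule and from the response rate.

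A reader might also infer that anyone enrolled with a lesion failing Section 8.1 can never respond. That is too broad. The cap is on subjects with non-measurable disease, so a patient with one failing lesion and one qualifying lesion is not capped.

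The affected group may be very small. If slices are contiguous and 5 mm thick (an assumption; the protocol states the skip but not the thickness), a roughly spherical lesion just over 1 cm crosses at least two slices, and only a flat lesion would fail. Recording two diameters also presupposes discernible edges. Experienced sites may apply full RANO at screening, the central office reviews baseline source documents (Section 8.4), and the registration forms, which are not in the documents, may already ask the question. These points lower the likely frequency. None of them makes the Section 8.1 definition an entry requirement.

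Finally, falling below 85% with a single patient mainly reflects a margin of 0.003, and any one unassessable patient would have the same effect. That is correct, and it is a reason not to read the figure as specific to this defect.

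**Conclusion.** The mismatch is real and does not depend on how often it occurs: criterion 3, followed exactly, admits patients who cannot meet the primary endpoint. Such a patient counts against the response rate and, on the face of the text, in the stage 1 rule. The position in the final rule is open.

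The power figures are conditional illustrations. They assume that the patients are counted, that the 30% rate describes scorable patients only, and that one to three such patients enter a cohort. On those terms power is 0.748 to 0.827 instead of 0.853. The documents do not support saying that the trial's power has in fact dropped below 85%. The direction is clear: type I error falls as well, so the risk is a false negative and not a false claim of activity. This is a recommended correction, not one on which the design stands or falls.

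**What to change.** 1. Reword criterion 3 to require measurable contrast-enhancing disease as defined for HGG RANO in Section 8.1. That means at least one lesion that meets every element there: bidimensional measurement, clear margins, the 1 cm x 1 cm minimum, and the two-slice condition with its 5 mm separation and 0 mm skip. Put the same item on the registration eligibility form if it is not already there.
2. Define evaluable in Section 11.2, and use one stated denominator for the stage 1 rule, the 5-of-23 rule and the response rate.

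The cost is a short amendment and possibly one form item. The baseline MRI is already required (Table 9.1), and N = 23 and both thresholds stay as they are. The downside is that a few borderline patients would be screened out of a rare population.
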